5.5 Sensitivity Analyses for the Primary Endpoints

Per the Kaplan-Meier method, subjects who count towards attrition will still contribute towards the primary effectiveness endpoint event rates until the time at which they are lost to follow-up (i.e. censored). Sensitivity analyses will be performed as follows.

Regarding attrition bias, baseline characteristics will be compared across attrition vs non-attrition subjects for each primary endpoint to determine if subjects counted towards attrition had a higher baseline risk profile. In addition, tipping-point analysis will be conducted to determine the lowest/highest assumed rate in attrition subjects (assuming they had been followed for 3-years) such that the alternative hypothesis is no longer met/failed. The probability of observing this tipping-point rate in the attrition subjects (assuming a true rate equal to that observed in non-attrition subjects) will then be calculated to determine the likelihood of observing this tipping-point rate in the attrition subjects.

5.6 Missing Data

Every effort will be undertaken to minimize missing data. In time-to-event outcomes drop-outs will be censored at the time of last follow-up, consistent with the Kaplan-Meier methodology. The last follow-up date will be the latest of the following dates for each subject: date of adverse event, randomization date, implant procedure date, discharge date, and follow-up visit date. Unless otherwise specified, no statistical techniques will be used to impute missing data for continuous or categorical outcomes. The number of subjects included in each analysis will be reported so that the reviewer can assess the potential impact of missing data.

For each primary and secondary endpoint, a sensitivity analysis will be conducted to assess the impact of censored data and will include a worst-case analysis.

5.7 Quality of life

Clinical trials increasingly recognize the value of including patient-reported outcome measures in their design. To understand the impact of atrial fibrillation related procedures and disease management on patient's quality of life, the quality-of-life instruments used for the trial will be the EQ-5D-5L and the 12-Item Short Form Health Survey (SF-12) for generic instruments. The EQ-5D is a descriptive system of health-related quality of life states consisting of five dimensions (mobility, self-care, usual activities, pain/discomfort, anxiety/depression) each of which can take one of five responses. The responses record five levels of severity (no problems/slight problems/moderate problems/severe problems/extreme problems) within a particular EQ-5D dimension. The SF-12 includes 12 dimensions with varying levels of response. Subjects will be asked to complete the questionnaires at the enrollment visit as well as at the 12-and 36-month follow-up visit.

5.8 Healthcare resource utilization

A formal health economics analysis may be completed as part of this trial, given meaningful clinical results are obtained. This will take into consideration any differences in survival, complication rates, quality of life, and resource utilization. The EQ-5D and SF-12 may be used to assess health utilities. We will capture health care utilization measures at all sites. These inputs may be used in health economics analysis performed beyond the scope of this Statistical Analysis Plan (SAP).

5.9 Interim Analyses

No formal interim analyses are planned for the purpose of stopping this study early for declaring effectiveness or for futility.

5.10 Changes to Planned Analyses

Any changes to the planned statistical analyses outlined in this plan will be documented in the clinical study reports along with a reason for any deviation.

6 VALIDATION

All clinical data reports generated per this plan will be validated per 90702587, Global WI: Clinical Data Reporting Validation.

7 PROGRAMMING CONSIDERATIONS

7.1 Statistical Software

Statistical analyses will be done using The SAS System Version 9.2 software or above (SAS Institute Inc., SAS Campus Drive, Cary, North Carolina 27513, USA. All rights reserved.). Other statistical software (e.g., R) may be used as necessary.

7.2 Format of Output

Results of analysis will be output programmatically to Word documents from SAS with no manual intervention. All output for the final statistical report will be in the form of a Word document containing tables, figures, graphs, and listings, as appropriate.

7.3 Rules and Definitions

Binary event rates (proportions) will be calculated on a per patient basis. Two-sided exact 95% confidence intervals will be given for all applicable endpoints presented as proportions.

For all time-to-event analyses, event-free subjects will be censored at the date of their last follow-up. The last follow-up date will be the latest of the following dates for each subject: date of adverse event, randomization date, implant procedure date, discharge date, and follow-up visit date.

Days to (event or censoring date) = (event or censor) date – randomization date.

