10.3. Study Completion, Withdrawal, or Lost to Follow-Up

While all efforts will be made to minimize attrition, subjects may withdraw from the study at any time, with or without reason and without prejudice to further treatment. Withdrawn subjects will not undergo any additional study follow-up, nor will they be replaced. All subjects enrolled in the clinical study (including those withdrawn from the clinical study or lost to follow-up) shall be accounted for and documented. When study subjects complete the study per the protocol requirements, their participation in the study is considered as complete, and they will be exited from the study.

If a subject withdraws from the clinical investigation, the reason(s) must be reported. If such withdrawal is due to problems related to device safety or performance, the investigator must ask for the subject's permission to follow his/her status/condition outside of the clinical study. This request needs to be documented in the subject file.

The sponsor may ask that withdrawn subjects are followed for information related to the safety of the device, if available.

Reasons for study exit will be captured in the EDC database and may include, physician discretion, subject choice to withdraw consent, lost to follow-up, or death. While study exit is discouraged, subjects may withdraw from the study at any time, with or without reason, and without prejudice to further treatment.

All applicable case report forms must be completed at study exit (i.e., withdrawal, death, study completion) and an "End of Study" form must be completed. Subjects who are "lost-to-

follow-up" must have documented at least three attempts to contact them prior to completion of the "End of Study" form. Should the subject continue to be unreachable, he or she will be considered to have withdrawn from the study with the primary reason of lost to follow up. Data collected up to the point of subject withdrawal may be used for study analysis unless local regulations prohibit its use.

At the point of study completion and/or withdrawal, all adverse events must be assessed by the investigator. These events must be closed or documented as chronic. For those events that have been assessed as related to the device, these should be followed through resolution if possible and consent has been provided by the subject for data collection on these events.

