11.14. Study Completion

All subjects will be followed through the completion of their 3-year follow-up visit, except for Screen Failure patients. An "End of Study" form will be completed to document the subject's study exit.

Once a study subject has exited the study, their participation in the study has ended. Appropriate eCRFs are completed indicating the status of the subject (i.e., end of study form). The table below provides information on the appropriate eCRFs to complete.

Table 11.14-1: Study Exit Data Collection Requirements

Type of Study Exit	Date to Use	Forms to complete		
Subject withdrawal	Date of subject withdrawal	 End of Study form Adverse Event (resolved/close any AEs or deem chronic) 		
Subject Lost to Follow-up	Date subject was last seen in office or last phone contact	End of studyAdverse Event (resolve/close any AEs or deem chronic)		
Subject Death	Date of Death	 Adverse Event (only one) with fatal outcome, resolve/close other AEs or deem chronic End of Study Form 		
Complete all protocol visits	Date of last study visit	 End of Study Form Adverse Event (resolve/close any AEs or deem chronic) 		
Screen Failure	Date the subject's ineligibility is determined	 "Screen Failure" designation on "Randomization" form within the "Baseline" folder End of Study Form Adverse Event (resolved/close any AEs or deem chronic) 		

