21.1. Reportable Events by investigational site to Boston Scientific

It is the responsibility of the investigator to assess and report to BSC any event which occurs from time of enrollment through 3-year follow-up including any of following categories:

- Unanticipated Adverse Device Effects/Unanticipated Serious Adverse Device Effects
- Serious Adverse Events regardless of cause Planned hospitalization for a pre-existing condition, or a procedure required by the clinical investigational plan, without serious deterioration in health, is not considered a serious adverse event.

In addition, the following events must also be reported:

- WATCHMAN FLX Device and/or WATCHMAN FLX index procedure related adverse events
- Adverse events related to protocol required testing (i.e., TEE or other LAA imaging)
- Adverse events where systemic embolism is suspected and/or confirmed, regardless
 of relationship to the WATCHMAN FLX Device.
- Adverse events related to WATCHMAN FLX Device (device thrombus, embolization, erosion, etc.).
- Adverse events related to the ablation procedure (if the procedure occurred after consent)
- Adverse events related to protocol required OAC or antiplatelet therapy
- All bleeding events regardless of relationship to the WATCHMAN FLX Device.
- All strokes (regardless of cause) and transient ischemic (TIA) regardless of relationship to the WATCHMAN FLX Device.
- New findings/updates in relation to already reported events

When possible, the medical diagnosis should be reported as the Event Term instead of individual symptoms.

If it is unclear whether or not an event fits one of the above categories, or if the event cannot be isolated from the device or index procedure, it should be submitted as an adverse event and/or device deficiency.

Any reportable event experienced by the study subject after informed consent and once considered enrolled in the study (as defined in study subject classification section) must be recorded in the eCRF.

Underlying diseases are not reported as AEs unless there is an increase in severity or frequency during the course of the investigation. Death should not be recorded as an AE but should only be reflected as an outcome of one (1) specific SAE (see Table 21.2-1 for AE definitions).

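### The censoring rule omits the study-exit and death dates that the trial collects, so event-free leavers can lose follow-up in which an event would still have counted; the upward bias in the 36-month rates is small

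*SAP*

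**What the plan says.** For all time-to-event analyses, SAP 7.3 states that "event-free subjects will be censored at the date of their last follow-up". That date is the latest of "date of adverse event, randomization date, implant procedure date, discharge date, and follow-up visit date". SAP 5.6 repeats the definition ("The last follow-up date will be the latest of the following dates for each subject"), and Protocol 13.3.7 has the same list.

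Protocol Table 11.14-1 assigns a date to each type of study exit. For withdrawal it is "Date of subject withdrawal"; for loss to follow-up, "Date subject was last seen in office or last phone contact"; for death, the date of death. None of these is among the five.

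Three other provisions bear on the point:

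- **Exit.** Protocol 10.3 says "At the point of study completion and/or withdrawal, all adverse events must be assessed by the investigator".
- **Event reporting.** Protocol 21.1 makes every stroke and every bleed reportable from enrollment through the 3-year follow-up. Protocol 21.4 and 21.7 require serious adverse events and deaths to be reported within three calendar days, not at the next visit.
- **Death.** Protocol 21.1 says "Death should not be recorded as an AE but should only be reflected as an outcome of one (1) specific SAE", and Table 11.14-1 asks for "Adverse Event (only one) with fatal outcome".

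Visits are at 3, 12, 24 and 36 months. The 36-month visit falls on or after day 1095, so completers are unaffected.

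**The concern.** The rule treats two otherwise identical leavers differently. Suppose a subject withdraws at month 23, having had a stroke at month 20. The stroke counts at month 20, because nothing in either document stops event counting at the last visit. Now suppose the same subject withdraws at month 23 with no event and no other adverse event since the 12-month visit. That subject is censored near month 12, and up to 11 months of event-free time leave the risk set. Of the five dates, the adverse event date is the one most likely to fall between late visits, so the length of follow-up depends partly on having an event. That is informative censoring, and it pushes 1 minus Kaplan-Meier upward.

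The same rule governs both primary endpoints and the secondary endpoint. At stake are the accuracy of the reported 36-month rates and, if attrition differs by arm, the differences that are compared with the 5% and 5.25% margins.

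**Working it through.** **The plan's own figures.** These reproduce, so the model below is the plan's model:

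- Farrington-Manning power is 85.9% at 680 per arm (efficacy) and 84.3% at 640 per arm (secondary), both as stated.
- 1360/0.85 = 1600.
- A rebuilt Kaplan-Meier/Greenwood simulation with 800 per arm and 10,000 trials gives 89.2% for efficacy (stated 89.3%) and 88.7% for the secondary endpoint (stated 88.9%).
- For safety, HR = ln(0.86)/ln(0.80) = 0.676. With about 245 events the power is 86.5% (stated 86.4%).

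The code in SAP section 10 censors each leaver at the simulated attrition time. That is exit censoring, so the stated 89.3% and 88.9% do not test the rule written in SAP 7.3.

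**Only the censoring date is changed.** Inputs are the plan's rates and attrition, constant hazards, and visits at 0, 3, 12, 24 and 36 months. Event-free leavers are cut back to their last visit, and events up to exit are all counted.

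1. Attrition hazard: c = −ln(1 − a)/3 per year.
2. Average time cut from an event-free leaver: with uniform exits it is (0.25² + 0.75² + 1² + 1²)/(2 × 3) = 0.44 years. The simulation gives 0.42, because exits fall slightly more in the early, shorter intervals.
3. With exponential times, event-free leavers number c × (person-years). The share of person-time lost is therefore 0.42c, and the estimated hazard is multiplied by k = 1/(1 − 0.42c).
4. Biased rate: F′ = 1 − (1 − F)^k.

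| Endpoint | True F | Attrition a | c | k | F′ by formula | Simulated |
|---|---|---|---|---|---|---|
| Efficacy | 10% | 15% | 0.0542 | 1.023 | 10.2% | 10.2% |
| Efficacy (assumed a) | 10% | 25% | 0.0959 | 1.042 | 10.4% | 10.4% |
| Secondary | 11% | 20% | 0.0744 | 1.032 | 11.3% | 11.3–11.4% |
| Safety, device | 14% | 20% | 0.0744 | 1.032 | 14.4% | 14.4% |
| Safety, control | 20% | 20% | 0.0744 | 1.032 | 20.6% | 20.6% |

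Censoring at exit returns the true rate in every scenario.

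**How far the size depends on assumptions (efficacy, 15% attrition):**

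- Half of leavers exit at their last visit: 10.1%.
- Only half of the events after the last visit are captured: 10.1%.
- None of those events is captured: 10.0%, no bias.
- Unrelated adverse events at 0.5 to 1 per year, which move the censoring date forward: about 10.2%.

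**Effect on the tests:**

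- *Equal attrition.* The efficacy difference stays at about 0, and power goes from 89.2% to 87.8%. At the null boundary (15% versus 10%) the difference becomes about 5.1 points. The pass rate falls from 2.9% to 2.2% in a run of 10,000 trials, and from 2.6% to 2.3% in a run of 60,000.
- *Unequal attrition (assumed).* At 15% versus 25%, the shift is 10.4% − 10.2% = about 0.2 points. At device 10% and control 20%, the null pass rate is 2.9% against 2.5% under exit censoring. The Monte Carlo error of each figure is √(0.025 × 0.975/10,000) = 0.16 points, so that gap is close to noise.

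**The case against.** The strongest case for leaving the rule alone is that it censors at the last documented assessment. A reader might infer from Protocol 10.3 that endpoint status is known up to the withdrawal date. The text does not say so: it goes on to have events closed or recorded as chronic, which tidies up reported events and does not establish that there were no others. At withdrawal, Table 11.14-1 asks only for the End of Study and Adverse Event forms. It lists no exit visit, stroke scale or bleeding review. Crediting an unassessed withdrawal date as event-free time could bias rates downward. This stands, and it shapes the fix.

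Other tempting inferences also go too far:

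- **That every Kaplan-Meier rate is inflated.** Bias needs events to be captured between the last listed date and exit. For subjects lost to follow-up, the exit date is the last contact; if that was a scheduled office or phone visit, nothing is lost. The cut-back is also to the latest adverse event where that is later than the visit.
- **That deaths go missing.** Death is an efficacy event and is dated as such. For bleeding, the fatal serious adverse event carries a listed date. Only the gap from its onset to death is lost, and the documents do not allow that gap to be sized.
- **That all of the 20% bleeding attrition is cut back.** It explicitly includes deaths. Assume 10% die, with fatal-event onset close to death, and 11% withdraw: 0.90 × 0.89 = 0.80 retained. Then c = 0.0388, k = 1.017, and 20% becomes 20.3%, not 20.6%.

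The plan also has tipping-point and worst-case analyses (SAP 5.5 and 5.6). These address unobserved outcomes. They neither restore follow-up that was observed nor change the primary estimate, so they do not answer the point.

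**Conclusion.** The concern holds as a small, avoidable bias in a stated rule. The written list omits dates that the trial collects, and the reporting rules are built to capture events between visits. The 36-month rates are therefore pushed up by at most about 0.2 to 0.3 points on 10 to 11%, 0.4 on 14% and 0.6 on 20%. The bias is about half that if half of leavers exit at a visit, and nil if no late events are captured. These figures assume constant hazards and the plan's attrition, with all leavers treated as withdrawals.

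A reader might infer that the non-inferiority conclusions are at risk. Under the plan's own assumption of equal attrition they are not: the arm differences are nearly unaffected, the tests are slightly conservative, and the 87.8% efficacy power still exceeds the stated 85.9%. The shift of about 0.2 points rests on an assumed 15% versus 25% split. It is about one-eighth of the standard error of the difference (about 1.6 points). The change is worth making because it is cheap and would align the analysis with the sponsor's simulation.

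**What to change.** In SAP 7.3, SAP 5.6 and Protocol 13.3.7, define the censoring date as the latest date on which endpoint status was ascertained. Add to the list:

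- the End of Study date: the withdrawal date where adverse events were assessed at exit, or the last office or phone contact if the subject was lost to follow-up;
- for the bleeding endpoints, the date of death.

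State that events count only up to that same date, so that events and event-free time share one cut-off. A withdrawal date without assessment of endpoint status should not be credited; such subjects stay censored at the last date on which status was known.

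The cost is a sentence in three places and one derived variable from dates already collected. The data must also show whether adverse events were assessed at exit; if the End of Study form does not record this, one item would have to be added. Where exit status is ascertained, the rule then matches the exit censoring in the SAP's simulation, so the sample size need not change.

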7.4 Clinical Events Committee

An independent Clinical Events Committee (CEC) will adjudicate all potential primary and secondary endpoints. CEC responsibilities, membership, meeting frequencies and procedures are outlined in the CEC charter. The CEC will make the final adjudication and classification of the

primary and secondary endpoints per the CEC charter, and the CEC determinations will supersede the site-reported data and sponsor classifications in all analyses of the primary and secondary endpoints.

7.5 Analyses of All Reported Serious Adverse Events

The proportion of subjects experiencing a serious adverse event (SAE), as well as the number of SAEs experienced, will be presented. These results will be presented both in aggregate as well as by SAE classification. The CEC classification will be used for events reviewed by the CEC, and the MEDRA LLT classification will be used for events not reviewed by the CEC.

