11.6. Randomization

Randomization will occur after all clinical and transthoracic echo criteria have been verified and the baseline assessment is complete. Randomization will occur no later than 30 days following consent. Subjects will be randomized 1:1 (Device: Control) and randomization will be stratified by sequential vs. concomitant planned ablation to help ensure balance of treatment assignments within the sequential and concomitant groups.

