23.3. Clinical Events Committee

A Clinical Events Committee (CEC) is an independent group of individuals with pertinent expertise that reviews and adjudicates important events for inclusion into the primary and secondary endpoints. The CEC will adjudicate events for all subjects beginning at the point of randomization. The events that the CEC will review for this study include:

- All cause stroke and TIA
- Systemic embolism
- Pericardial Effusion requiring intervention
- All cause death
- ISTH major bleeding and clinically relevant non-major bleeding
- Other events, at the discretion of Boston Scientific

The CEC will review a safety event dossier, which may include copies of subject source documents provided by study centers and confirm inclusion of the event into the primary and secondary endpoints. Committee membership may include practitioners of electrophysiology, interventional cardiology, neurology, and neuroradiology. CEC responsibilities, qualifications, membership, and committee procedures are outlined in the CEC charter.

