1 PROTOCOL SYNOPSIS

Comparison	Comparison of An ti coagulation with Left Atrial Appendage Closure after AF Ablatio n (OPTION)						
Study Objective(s)	The primary objective of this study is to determine if left atrial appendage closure with the WATCHMAN FLX Device is a reasonable alternative to oral anticoagulation following percutaneous catheter ablation for high risk patients with non-valvular atrial fibrillation.						
Planned Indication(s) for Use	The planned indication for use within the OPTION study is as follows: The WATCHMAN and WATCHMAN FLX Device are indicated to reduce the risk of thromboembolism from the left atrial appendage in subjects with non-valvular atrial fibrillation who: • Are at increased risk for stroke and systemic embolism based on CHA2DS2-VASc scores following catheter ablation of atrial fibrillation; and • Are deemed to be suitable for anticoagulation therapy Note: In countries where CE mark applies, the OPTION indication is within the CE mark approved Indication for Use.						
Study Design	This study is a prospective, randomized, multi-center, global investigation to determine if left atrial appendage closure with the WATCHMAN FLX Device is a reasonable alternative to oral anticoagulation in patients after AF ablation.						
Planned Number of Subjects	A maximum of 1600 subjects will be randomized in the study. Note the total number of enrolled patients is expected to exceed the number of randomized subjects since sites without WATCHMAN FLX experience are required to perform two roll-in cases. A maximum of 260 patients will be treated in the roll-in phase of the study, including approximately 130 roll-in subjects in the United States. The roll-in cohort will be analyzed separately from the primary cohort of randomized subjects.						
Planned Number of Centers / Countries	Up to 150 investigational centers worldwide						
Primary Effectiveness Endpoint	WATCHMAN therapy is non-inferior for the occurrence of stroke (including ischemic and/or hemorrhagic), all cause death, and systemic embolism at 36 months.						

Comparison of Anticoagulation with Left Atrial Appendage Closure after AF Ablation (OPTION)						
Primary Safety Endpoint WATCHMAN therapy is superior for non-procedural bleeding throu months (ISTH major bleeding and clinically relevant non-major blee						
Secondary Endpoint	WATCHMAN therapy is non-inferior for ISTH major bleeding at 36 months (including procedural bleeding)					

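### Serious adverse events outside CEC review are to be tabulated at MedDRA's finest coding level with no grouped summary, which can obscure a difference between arms by event type

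*SAP*

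**What the plan says.** SAP 7.5 is the whole of the SAE analysis plan. It sets the measures: "The proportion of subjects experiencing a serious adverse event (SAE), as well as the number of SAEs experienced, will be presented". It sets the layout: "These results will be presented both in aggregate as well as by SAE classification". It then names two sources for the classification. For adjudicated events, "The CEC classification will be used for events reviewed by the CEC". For everything else, "the MEDRA LLT classification will be used for events not reviewed by the CEC".

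Protocol 23.3 lists what the CEC reviews: stroke and TIA, systemic embolism, pericardial effusion that needed intervention, death, "ISTH major bleeding and clinically relevant non-major bleeding", and further events if the sponsor chooses. SAEs outside that list fall under the MedDRA rule.

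Neither document mentions the preferred term, the high level term, the system organ class, a MedDRA version or any other grouping of related terms. SAP 7.5 does not say that the tables are by randomized group, although that is the natural reading.

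**The concern.** LLT is read here as MedDRA's lowest level term, the entry layer at which a reported event is coded. That layer includes synonyms; the preferred term above it gathers them into one medical concept. If the summary table has one row per lowest level term, its rows depend partly on how each site worded the event, and the SAP allows up to 150 centers worldwide.

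The plan then gives two views of SAEs that the CEC does not review: one overall total, and rows at the finest level. Nothing is planned in between. Unless the sponsor refers them to the CEC, events such as heart failure, infection and pericardial effusion without intervention are seen by type only in those rows. An excess in one arm could be spread over several small rows, none of them striking. Protocol 20.4 says it is not known whether combining ablation and implant raises the risk of adverse events, so a readable table by event type has some value in this trial.

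**Working it through.** The documents state no figure on this point, so there is nothing to reproduce. The calculations below only illustrate how much a row can lose.

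**Inputs from the documents.** "A maximum of 1600 subjects will be randomized in the study" (SAP synopsis). Allocation is 1:1 (Protocol 11.6), so 1600/2 = 800 per arm.

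**Assumed inputs.** The event rates, the number of synonymous terms and how evenly events divide among them. The documents give none of these.

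**Counts (Fisher's exact test, two-sided, 800 per arm).**

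- Assume one medical event in 32 v 16 subjects (32/800 = 4%, 16/800 = 2%). On one row, p = 0.027.
- Even split over three terms: 32/3 = 10.7 and 16/3 = 5.3, so rows of about 11 v 5, p = 0.208. With two such rows, the third holds 32 − 22 = 10 v 16 − 10 = 6, which is weaker still.
- Uneven split with one dominant term holding 28 v 14: p = 0.041. Little is lost.
- A larger excess, 48 v 24 (6% v 3%): p = 0.005 on one row; two rows of 24 v 12, p = 0.062 each; three rows of 16 v 8, p = 0.149 each.

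**Range.** The chance that a given row shows a nominal two-sided 5% difference is

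Φ[(|p₁ − p₂| − 1.96·se₀)/se₁], with se₀ = √[2p̄(1 − p̄)/n], se₁ = √[p₁(1 − p₁)/n + p₂(1 − p₂)/n], p̄ = (p₁ + p₂)/2 and n = 800.

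For 2% v 4%: se₀ = √(2 × 0.03 × 0.97/800) = 0.00853, se₁ = 0.00851, giving Φ[(0.02 − 0.01672)/0.00851] = 65%. Divide both rates by 3 for an even three-way split: se₀ = 0.00498, se₁ = 0.00497, giving Φ[(0.00667 − 0.00975)/0.00497] = 27%.

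| Assumed rates | One row | Split over 2 | Split over 3 | Split over 5 |
|---|---|---|---|---|
| 2% v 4% | 65% | 38% | 27% | 18% |
| 3% v 6% | 83% | 53% | 38% | 25% |
| 5% v 8% | 68% | 39% | 28% | 18% |
| 6% v 10% | 84% | 53% | 38% | 25% |

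Under even splits, 65–84% on one row falls to 18–53% per row. Even splitting is the unfavourable assumption: the more one term dominates, the closer the result stays to the first column. The p-values are only a yardstick for visibility, since the SAP runs no such test.

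**The case against.** A reader might infer that the lowest-level-term table is the only safety comparison for these events, or that it will hide differences. The documents do not support either reading.

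- The proportion of subjects with an SAE and the SAE count are also presented in aggregate, and coding level does not change them. An independent data monitoring committee also reviews safety (Protocol 23.4).
- The events that matter most for this device and comparator go to the CEC and keep its classification. Device thrombus and AF recurrence have their own analyses (SAP 3.4).
- Wording is partly controlled. Protocol 21.1 instructs sites: "When possible, the medical diagnosis should be reported as the Event Term instead of individual symptoms". Physicians in the sponsor's safety group classify events (Protocol 23.1).
- The tables are descriptive and no success criterion draws on them. The documents do not describe the MedDRA hierarchy or say how many terms would be used, so splitting is possible rather than shown.
- Regrouping is possible at any time, and SAP section 5 allows further analyses where appropriate.

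The first four limit the size of the point, and all four stand. They do not remove it. Asking for a diagnosis rather than symptoms does not merge synonyms for one diagnosis. The role given to the safety physicians is not tied to the rows of this table. The stated row level is still the finest one. A general allowance for further analyses commits to no grouped table, and a grouping chosen after the data are seen is weaker than one fixed beforehand.

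**Conclusion.** The point holds as a minor reporting weakness. For SAEs that the CEC does not review, SAP 7.5 fixes the finest coding level as the row level and plans nothing between those rows and the overall total. One medical event can therefore be spread over several synonymous rows, which can obscure a difference between arms by event type.

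Its size cannot be established from the documents. The illustrations rest on assumed rates and splits: an even three-way split takes p from 0.027 to 0.21 on a row, while a dominant term leaves it at 0.041. The argument also assumes the usual MedDRA structure, in which several lowest level terms can map to one preferred term.

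It would be wrong to conclude that safety reporting as a whole is compromised or that the trial's result is at risk. The aggregate SAE results, the CEC-classified events, the primary and secondary endpoints and the success criteria are untouched.

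**What to change.** In SAP 7.5, for events not reviewed by the CEC, replace the lowest-level-term classification with: *MedDRA system organ class and preferred term, by randomized treatment group, counting each subject once per term*. Leave the CEC classification rule unchanged for the events it covers, so that each event still has one source of classification. Keep lowest level terms in the listings.

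The cost is one SAP sentence. The preferred term and system organ class come with the coding already planned, so no new data or recoding is needed. The only downside is some loss of granularity in the summary table, and the listings retain that detail.
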